5.1 Subject informed consent

Prior to performing any study procedures, the Investigator (or designated personnel) will ensure that the subject is given full and adequate oral and written information about the study and the subject must sign the informed consent form (ICF), as described in Section 11.2.1.

Based upon the results of Study MT-8554-A01, the dose is changed from 10 mg to 5 mg. The Investigator (or designated personnel) will ensure that the participating subject must provide reconsent to continue the study and the subject who reconsent to continue the study will receive MT-8554 5 mg.

5.2 Description of study phases

5.2.1 Open-label extension

5.2.1.1 Visit 1: Treatment period (Week 12)

Subjects who have completed Study MT-8554-A01 and comply with eligibility criteria will be enrolled in this study. Subjects will be requested to attend the clinic after a 6-hour fasting period (except for water).

Signed informed consent will be obtained before any procedures are performed. The following assessments will be performed. (Assessments already carried out at Week 12 of Study MT-8554-A01 will not be repeated; refer to Table 1 for further details):

- Signed informed consent
- Inclusion/exclusion criteria
- Physical examination (see Section 6.5.1)
- Breast examination
- Body weight
- Vital signs (including sitting blood pressure, pulse rate, and tympanic body temperature)
- 12-lead ECG
- Routine laboratory evaluations (hematology, biochemistry, coagulation, and urinalysis)
- Reproductive hormone assessments: E2, LH, and FSH
- Transvaginal ultrasound and endometrial biopsy (for subjects with a uterus)
- PHQ-8 and GAD7
- MENQOL assessment

- Dispensing MT-8554
- Drug Accountability for Study MT-8554-A01
- AE and concomitant medication recording.
- Diary compliance [REDACTED] reminder

5.2.1.2 Visits 2 to 5 (Treatment period, Weeks 20, 28, 40, and 52)

Subjects will attend visits every 8 weeks between Visits 1 and 3 (Weeks 12, 20, and 28) and every 12 weeks between Visits 3 and 6 (Weeks 28, 40, 52, and 64). The following assessments will be performed (refer to Table 1 for further details):

- Physical examination (see Section 6.5.1)
- Body weight (Visit 4 only)
- Vital signs (including sitting blood pressure, pulse rate, and tympanic body temperature)
- 12-lead ECG (Visit 4 only)
- Routine laboratory evaluations (hematology, biochemistry, coagulation, and urinalysis)
- PHQ-8 and GAD7 (Visit 3 only)
- MENQOL (Visit 3 only)
- Review VMS diary (re-educate subject if necessary)
- Dispensing MT-8554 (Visits 2 to 5 only)
- Drug Accountability
- AE and concomitant medication recording.
- Diary compliance [REDACTED] reminder

5.2.1.3 Visit 6: EOT (Week 64 or early termination)

Subjects will attend the last visit of the treatment period and the following assessments will be performed (refer to Table 1 for further details):

- Physical examination (see Section 6.5.1)
- Breast examination
- Body weight
- Vital signs (including sitting blood pressure, pulse rate, and tympanic body temperature)
- 12-lead ECG
- Routine laboratory evaluations (hematology, biochemistry, coagulation, and urinalysis)
- Transvaginal ultrasound and Endometrial biopsy (for subjects with a uterus)
- Reproductive hormone assessments: E2, LH, and FSH
- PHQ-8 and GAD7
- MENQOL
- VMS diary collection
- Drug Accountability
- AE and concomitant medication recording.

5.2.2 Follow-up

5.2.2.1 Visit 7: Follow-up Visit (FU, Week 68 or 4 weeks after early termination)

Subjects who complete the study (or subjects who withdraw from treatment early) will be telephoned by the Investigator (or designee) 30 days after EOT, for a Follow-up visit. Information on any new AEs, follow-up on existing AEs, and prior/concomitant medication will be recorded.

5.2.3 Post-study access to treatment

MT-8554 will not continue to be available to subjects following completion or termination of the study, in accordance with the study information given to the subjects.

5.2.4 Phone Calls to Subject

Sites will make periodic calls to subjects at a minimum of every 4 weeks where no in clinic visits occur, to ensure subject compliance with daily VMS diary completion. [REDACTED] AEs reported during the calls will be documented as applicable.

5.2.5 Unscheduled visits

An unscheduled visit is defined as any visit to the Investigator site outside of the protocol specified study site visits due to safety reasons or when a repeat test and/or measurement is required (e.g., obvious measurement errors, measuring device failure, confirmation of out-of-range results), where the subject is seen by study personnel.

Additional unscheduled samples for safety assessments may be performed at the discretion of the Investigator, if deemed necessary. All unscheduled visits and assessments performed during the visits will be recorded in the eCRF.

6 STUDY PROCEDURES

Procedures will be performed according to the Schedule of Assessments (Table 1). A priority order will be in effect when more than 1 assessment is required at a particular time point and this will be described in a separate document. Time windows for relevant assessments will also be described in a separate document.

6.1 Informed consent form

The Investigator or designee will fully explain the nature of the study to subjects using the Institutional Review Board (IRB)-approved informed consent document. When the subject agrees to participate in the study, the subject must voluntarily sign a consent form prior to the initiation of any study procedures. A copy of the signed and dated informed consent document will be given to the subject. The signed and dated original consent form will be retained by the Investigator. Informed consent will be obtained from all subjects. A subject cannot be entered into the study until he/she has signed and dated the consent form.

The Investigator or designee is responsible for ensuring that the subject understands the risks and benefits of participating in the study, including answering any questions the subject may have throughout the study and sharing any new information in a timely manner that may be relevant to the subject's willingness to continue his/her participation in the study.

6.2 Demography

The subject characteristics (date of birth, sex, weight, height, and race) have been recorded at Screening in Study MT-8554-A01.

6.3 Medical history

The medical, drug, smoking, alcohol, and surgical history have been recorded at Screening in Study MT-8554-A01. Medical/surgical history includes any medical condition or surgical history prior to Screening.

6.4 Concomitant medication

Concomitant medication is defined as any medication, other than study medication, which is taken during the study, including prescription and over-the-counter medications. All concomitant medications taken while the subject is participating in the study will be recorded.

Concomitant medication will be given only if deemed necessary by the Investigator or the subject's personal physician.

6.4.1 Prohibited medication

Subjects must not participate in any other clinical study involving administration of another investigational study medication from Visit 1 through the final Follow-up assessment.

Subjects must not take any prescribed or non-prescribed systemic or topical medication (including herbal or dietary supplements) known to possibly have an effect on VMS or sleep during the study. Such drugs include, but are not limited to estrogen, gabapentin, clonidine, progestin, black cohosh, soy, phytoestrogens, sedatives, and hypnotics.

Antidepressants prescribed for the treatment of VMS and paroxetine are prohibited during the study period. Other antidepressants are permitted as long as the doses are stable and no dose adjustments are anticipated during the study period.

6.4.2 Rescue medication

There is no known antidote to MT-8554. In the case of significant AEs, appropriate medical management will be provided by site staff.

6.5 Safety assessments

Please refer to Section 8 for details of AE management.

6.5.1 Physical examination

The physical examination will be performed at each visit and will consist of a routine assessment of the following body systems: abdominal, cardiovascular, general appearance, respiratory, and 'other'.

6.5.2 Breast examination

A breast examination (symmetry of breast shape, contour of breast, appearance of skin, nipple, areola, lymph nodes status, presence and characterization of lesions) will be performed at Week 12 and Week 64 or early termination. The Investigator or designated study staff will perform a clinical examination and record in the eCRF.

If the breast examination is found to be 'abnormal clinically significant', the subject is instructed to discontinue the study drug and proceed with follow-up management per standards of care including mammogram, ultrasound and biopsy. If breast lesion is considered benign after complete evaluation of subject and investigations, subject will be allowed to resume the study medications within 6 weeks of interruption of study medication.

6.5.3 Vital signs

Subjects' vital signs (sitting blood pressure, pulse, and tympanic body temperature) will be taken at each visit. Subjects will undergo an assessment of blood pressure at each visit using a blood pressure recording device with an appropriate cuff size and with the subject in a sitting position. The same arm will be used for all measurements. Pulse rate and tympanic body temperature will also be measured. An infrared ear thermometer will be used to measure tympanic body temperature.

The Investigator will perform an overall evaluation for safety purposes and the recording will be reported as 'normal', 'abnormal clinically significant (CS)', or 'abnormal not clinically significant (NCS)'.

Abnormalities of clinical significance will be reported as AEs. Repeat measurements will be performed if needed.

6.5.4 Electrocardiogram

A 12-lead ECG will be performed after the subject has rested for at least 5 minutes in the supine position. The Investigator will perform an overall evaluation of the ECG for safety purposes and the recording will be reported as 'normal', 'abnormal CS', or 'abnormal NCS'. Abnormalities of clinical significance will be reported as AEs. Repeat measurements will be performed if needed.

6.5.5 Transvaginal ultrasound

For subjects who have a uterus, a transvaginal ultrasound will be performed at Week 12 and Week 64 or early termination to measure endometrial thickness. The scans will be performed locally by qualified personnel and blinded review will be conducted centrally. Procedures for the handling of these assessments will be described in full in separate documents.

6.5.6 Endometrial biopsy

For subjects who have a uterus, an endometrial biopsy will be performed at Week 12 and Week 64 or early termination to assess endometrial hyperplasia. The biopsy samples will be processed and assessed by central laboratory. Biopsy results will be adjudicated by a committee consisting of 3 independent expert pathologists, who will remain blinded. Procedures for the handling of these assessments and adjudications will be described in full in separate documents.

Pelvic examination will be performed only with the endometrial biopsy at Visits 1 and 6.

6.5.7 Routine laboratory evaluations

Blood and urine samples will be collected for routine clinical laboratory safety evaluations according to Table 1. The laboratory safety evaluations performed during the study are presented in Table 2.

Additional laboratory safety evaluations will be performed at other times, if judged to be clinically appropriate, or if the ongoing review of the data suggests a more detailed assessment of laboratory safety evaluations is required. Any changes to the scheduled times of laboratory safety tests will be agreed with the Sponsor and documented in the Trial Master File.

The Investigator will perform a clinical assessment of all laboratory data. The Investigator will record the assessment as 'normal', 'abnormal CS', or 'abnormal NCS'. Lab test abnormalities of clinical significance will be reported as AEs. Repeat lab tests or measurements will be performed for abnormal results.

Table 2 Routine laboratory evaluations

Hematology:	
Hemoglobin	Mean corpuscular hemoglobin
Hematocrit	Mean corpuscular hemoglobin concentration
Platelet count	Mean corpuscular volume
Red blood cell count	White blood cell count and differential
Biochemistry:	
Alkaline phosphatase	Cholesterol
Aspartate aminotransferase	Triglycerides
Alanine aminotransferase	High density lipoprotein-cholesterol
Gamma-glutamyl transpeptidase	Low density lipoprotein-cholesterol
Potassium	Protein (total)
Sodium	Albumin
Chloride	Creatine kinase
Inorganic phosphate	Creatinine
Glucose	Follicle Stimulating Hormone ¹
Urea	Estradiol ¹
Bilirubin (direct and total)	Luteinizing hormone ¹
Coagulation:	
Prothrombin time	Activated partial thromboplastin time
International normalized ratio	
Urinalysis:	
Specific gravity, pH, protein, glucose, ketones, urobilinogen, blood	
Microscopic examination ²	

¹ Visit 3 and Visit 6 (end of treatment [EOT], Week 64, or early termination) only.

² Performed only if required, based on urinalysis results.

Blood samples will be analyzed by [REDACTED] using standard methods. Procedures for the handling of samples will be described in full in a separate document.

6.6 Safety-related questionnaires

6.6.1 Eight-Item Patient Health Questionnaire⁶

The PHQ-8 is a self-rated questionnaire assessing current depressive symptoms based on 8 out of 9 criteria of the Diagnostic and Statistical Manual of Mental Disorders, 4th Edition (DSM-IV). See APPENDIX 1 for an example of the PHQ-8.

6.6.2 Generalized Anxiety Disorder-7⁷

The GAD7 is a self-rated questionnaire assessing current anxiety levels. See APPENDIX 2 for an example of the GAD7.

6.7 Efficacy assessments

6.7.1 Subjective vasomotor symptoms

Subjects will be asked to record frequency and severity of VMS in an electronic diary beginning at Visit 1 and throughout the open label treatment period. See APPENDIX 3 for an example of the VMS diary.

VMS diaries will be provided by the Sponsor and given to subjects by clinic personnel, with instructions on its use. See Section 9.1 for further information related to VMS diary data collection and transfer.

Definitions of VMS severity levels (per 2003 draft FDA guidance) are provided in Table 3.

Table 3 VMS Severity Levels

Severity	Definition
Mild	Sensation of heat without sweating
Moderate	Sensation of heat with sweating, able to continue activity
Severe	Sensation of heat with sweating, causing cessation of activity

Abbreviations: VMS=vasomotor symptoms

6.7.2 Menopause-Specific Quality of Life⁶

The MENQOL is self-administered and consists of a total of 29 items in a Likert-scale format. Each item assesses the impact of 1 of 4 domains of menopausal symptoms, as experienced over the last month: vasomotor (items 1–3), psychosocial (items 4–10), physical (items 11–26), and sexual (items 27–29). Items pertaining to a specific symptom are rated as present or not present, and if present, how bothersome on a 0 (not bothersome) to 6 (extremely bothersome) scale. Means are computed for each subscale by dividing the sum of the domain's items by the number of items within that domain. Non-endorsement of an item is scored a “1” and endorsement a “2,” plus the number of the particular rating, so that the possible score on any item ranges from 1 to 8. See APPENDIX 4 for an example of the MENQOL.

7 STUDY MEDICATIONS, TREATMENT AND DOSING REGIMEN

7.1 Investigational Medicinal Product

7.1.1 Drug product

MT-8554 capsules are white capsules with no identifying mark. MT-8554 capsules contain [REDACTED] mg of MT-8554 drug substance per capsule.

Bulk capsules will be packed in [REDACTED]

Individual subject doses will be packed in [REDACTED]

MT-8554 capsules are manufactured, tested, and released according to Good Manufacturing Practice. All labeling will comply with applicable regulatory requirements. The Sponsor will provide the necessary documentation, such as a Certificate of Compliance or Quality Control release document.

7.1.2 Study drug supply

The Sponsor will provide MT-8554 to each site for each subject for the duration of their participation in the study. The Investigator, Study Nurse, or hospital pharmacy will dispense MT-8554 capsules at study visits according to protocol. A sufficient quantity of the appropriate strength MT-8554 capsules ([REDACTED] mg) will be dispensed consistent with each subject's daily dosage requirement. Subjects should be instructed to bring their study medications with them to each visit and the Investigator or Study Nurse will perform a capsule count to ensure the subject has a sufficient supply of medication to last until the next scheduled visit. Subjects must return all study drugs remaining in their possession to study staff at Visit 6 (EOT, Week 64, or early termination).

7.1.3 Formulation, packaging, site storage, and labeling (MT-8554)

Capsules will be provided in [REDACTED] mg capsules. Study drug will be provided to the study sites [REDACTED] and should be stored according to the study medication clinical label.

MT-8554 capsules must be dispensed in [REDACTED]. Subjects will be instructed to store the medication per the study medication clinical label.

Documentation for MT-8554 capsules will include, but may not be limited to, the following information:

- Receipt date
- Description of drug package, and drug product
- Lot/Batch/Code/other
- Expiration and Manufacturing dates
- Dispensing information
- IND number
- Certificate of Compliance

7.1.4 Shipping, receipt, handling and storage

On receiving a shipment of finished study medication at the Investigator site, the Investigator or designee will conduct an inventory check and complete a supplies receipt document, the original of which will be retained at the Investigator site; a copy must be returned to the Sponsor or designee. The Investigator or designee will maintain a record of all study medication received and returned.

Study medication at the Investigator site will be stored according to the conditions stated on the study medication clinical label in a locked, restricted-access area. A temperature log recording the daily continuous temperature of the storage area will be maintained (including weekends). Any study medication storage temperature excursions will be reported to the Sponsor.

7.1.5 Dispensing

At each visit, the Investigator or designee will provide the subject with the allocated dose. A record of the study medication dispensed to each subject will be maintained by the Investigator or designee in a Drug Accountability Log. Any opened bottles will not be re-dispensed.

7.1.6 Study drug accountability

The Investigator or designee must maintain an accurate record of the shipment and dispensing of study drug in a Drug Accountability Log. Drug accountability will be noted by the field monitor during site visits and at the completion of the study. Subjects will be asked to return all unused study drug and packaging on a regular basis, at the end of the study or at the time of study treatment discontinuation.

7.1.7 Disposal and destruction

At study close-out, and as appropriate during the course of the study, the site will return all used and unused study drug, packaging, drug labels, and a copy of the completed Drug Accountability Log to the Sponsor's designated monitor or to the address provided in the Investigator Binder at each site.

The study drug supply may only be destroyed at the designated Sponsor facility or third party, as appropriate.

7.2 Dosing

Subjects are to self-administer study medication once daily at least 2 hours after starting their evening meal and approximately 30 minutes before bedtime.

MT-8554 capsules should be swallowed whole with approximately 8 ounces of water (subjects may drink an additional 8 ounces of water if they have difficulty swallowing the capsules). The capsules must not be chewed, crushed or divided.

7.2.1 Compliance

The prescribed dosage, timing and mode of administration of study medication may not be changed. Any departures from the intended dose regimen must be recorded in the eCRF.

Study medication accountability and subject compliance will be documented throughout the OLE period using study medication dispensing and return record logs.

Subjects will be asked to return all unused medication including empty and partially used bottles. Study medication dispensed at the previous visit will be collected by the site and compliance will be assessed by counting the returned drug.

Non-compliance is defined as taking [REDACTED] of study medication during any visit.

7.3 Subject identification

Each subject will be identified by the unique Subject Number that was assigned to them at the Screening visit of Study MT-8554-A01.

7.4 Procedures for assigning subjects to treatment groups

In this open-label extension study, all subjects who completed Study MT-8554-A01 and who meet criteria for enrolment in Study MT-8554-A02 will receive MT-8554 (was 10 mg initially, switched to 5 mg) for 52 weeks. Study drug will be administered once daily before bedtime (Section 3.1).

Based upon the results of Study MT-8554-A01, the dose is changed from 10 mg to 5 mg. All participating subjects who reconsent to continue the study will receive MT-8554 5 mg. An unscheduled visit will be used to accommodate such change in study drug dose.

8 ADVERSE EVENT MANAGEMENT

All AEs and SAEs will be recorded in the source documents. All AEs and SAEs that occur from the time the informed consent is signed until the end of the Safety Follow-up period (30 days after the last treatment visit) will be recorded in the eCRF. Even if the AE is assessed by the Investigator as not related to study medication, its occurrence must be recorded in the source documents and eCRF. AEs will be classified as 'treatment-emergent' if they arise following the first administration of study medication in the OLE period or if an AE which is continued from the preceding trial (Study MT-8554-A01) increases in severity following the first administration of study medication in the OLE period.

At each study visit, after the subject has had an opportunity to spontaneously mention any problems, the Investigator should inquire about the occurrence of AEs. The questioning should be open-ended and non-leading.

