8.3 Severity of adverse events

The severity of AEs will be classified according to the following criteria:

Mild: The event is transient and easily tolerated by the subject.

Moderate: The event causes discomfort and interferes with the subject's general condition.

Severe: The event causes considerable interference with the subject's general condition and may be incapacitating.

To ensure no confusion or misunderstanding of the difference between the terms 'serious' and 'severe', which are not synonymous, the following note of clarification is provided:

The term 'severe' is often used to describe the severity of a specific event (as in mild, moderate, or severe myocardial infarction); the event itself, however, may be of relatively minor medical significance (such as severe headache). This is not the same as 'serious', which is based on patient/event outcome or action criteria usually associated with events that pose a threat to a patient's life or functioning. Seriousness (not severity) serves as a guide for defining regulatory reporting obligations.

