10.3 Statistical analysis

10.3.1 General considerations

A SAP containing definitions of analysis populations and baseline points, detailed data handling, analysis methods, detailed methods and criteria for the interim analysis, and outputs (tables, figures and listings) will be developed and approved prior to database lock. Additional analysis may be performed if deemed necessary. Any deviations from the planned analysis will be described and justified in a separate document and in the CSR.

The statistical analysis will be performed using SAS® Version 9.2 or higher. The Safety population will be used for all analyses and summaries. Point estimates will have 2-sided 95% CIs where applicable.

Where appropriate, data will be summarized descriptively (frequency and percent will be summarized for categorical variables; mean, standard deviation, median, minimum, and maximum will be presented for continuous variables) by study visit and by treatment group.

All individual subject data will be listed, where applicable. The baseline value of Study MT-8554-A02 is the last valid values prior the first dose of Study MT-8554-A02. The baseline value of Study MT-8554-A01 and Study MT-8554-A02 will be used as appropriate.

The Study MT-8554-A01 data are combined with Study MT-8554-A02 data for summary tables and graphs as needed.

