10.3.4.1 Adverse events

AEs are considered as treatment emergent if they occur after the first dose administration of study medication of Study MT-8554-A02 or if a pre-dose event increases in severity following dosing. The frequency and incidence of TEAEs will be summarized by System Organ Class (SOC) and Preferred Term (PT), by treatment group and overall. TEAEs will be summarized by treatment, by relationship to study medication and by maximum severity as well. Serious TEAEs and TEAEs leading to study medication discontinuation will be summarized in tables. All AE will be presented in a data listing.

Physical examination data will be listed by subject. Changes in physical examinations will be described in the text of the CSR.

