### 7.3.2.3 Duration of the AE and Time to the AE

Duration of the AE and time to the AE occurrence from start of study A02 medication will be calculated and presented in days, where AE duration = AE stop date – AE start date + 1 and the time to the AE occurrence = AE start date – first study A02 dose date + 1.

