### **8.2 Safety Assessments**

#### **8.2.1 Adverse Events**

The frequency and incidence of TEAEs will be summarized by System Organ Class (SOC) and Preferred Term (PT) by treatment of study A01 and overall.

Following summaries will be presented:

- Overall summary of TEAE (Table 14.3.1.1)
- TEAEs by SOC and PT (Table 14.3.1.2)
- TEAEs by SOC, PT and time of onset (Table 14.3.1.3)
- TEAEs by SOC, PT and severity (Table 14.3.1.4)
- TEAEs leading to discontinuation of study medication by SOC and PT (Table 14.3.1.5)
- Serious TEAEs by SOC and PT (Table 14.3.1.6)
- TEAEs by SOC, PT and relationship (Table 14.3.1.7)
- [REDACTED]

- Adverse drug reactions by SOC and PT (Table 14.3.1.9)
- Serious adverse drug reactions by SOC and PT (Table 14.3.1.10)
- TEAEs by SOC and PT for AEs with frequency  $\geq 3\%$  (or 5%) (Table 14.3.1.11)
- [REDACTED]

For each of the summaries will be done at the subject level - multiple occurrences of the same event within a subject will be counted once in the summaries by SOC and PT; multiple occurrences of the same event within a subject will be counted once in the maximum intensity category (severe > moderate > mild) and/or maximum drug relationship category (reasonable possibility, no reasonable possibility) and/or the earliest occurrence. If intensity or relationship is found to be missing the most severe occurrence will be imputed for that particular summary.

All AEs for each subject, including multiple occurrences of the same event, will be presented in full in a comprehensive listing including subject number, severity, seriousness, action taken, outcome, relationship to treatment, onset/stop date and duration.

Deaths that occur during the study will be listed in a data listing. The data listings for serious TEAE and TEAE leading to discontinuation will be generated as well.

[REDACTED]

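### Adverse events that began before the first A02 dose and later stop study drug or turn serious at unchanged severity are missing from the discontinuation and serious-event tables and their listings

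*Protocol*

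**What the plan says.** The sole primary objective is long-term safety and tolerability (Protocol 2.1.1).

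**TEAE rule.** Protocol 8 counts an event as treatment-emergent if it arises after the first open-label dose, or if "an AE which is continued from the preceding trial (Study MT-8554-A01) increases in severity following the first administration of study medication". Protocol 10.3.4.1 agrees on the starting point: "AEs are considered as treatment emergent if they occur after the first dose administration of study medication of Study MT-8554-A02". Its clause for earlier events is likewise tied to severity alone: "or if a pre-dose event increases in severity following dosing". SAP 7.3.2.1 keeps severity as the only worsening trigger but does not say which study's first dose is meant. SAP 7.3.2.3 measures "time to the AE occurrence from start of study A02 medication".

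**Outputs.** In SAP 8.2.1 the discontinuation table is titled "TEAEs leading to discontinuation of study medication by SOC and PT (Table 14.3.1.5"). Table 14.3.1.6 covers serious TEAEs, and the matching listings are also TEAE-only. The same section plans adverse drug reaction tables (14.3.1.9 and 14.3.1.10), a full listing of all AEs, and a listing of deaths. SAP 7.3.2.2 defines an adverse reaction from AEs, not from TEAEs. SAP 8.1.1 tabulates discontinuation reasons by A01 arm.

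**Pooling.** Protocol 10.3.1 says: "The Study MT-8554-A01 data are combined with Study MT-8554-A02 data for summary tables and graphs as needed". No readable AE table in the SAP uses this.

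**The concern.** The last A01 visit is the first A02 visit, so women can enter with events still running from 12 weeks of blinded treatment. An event that persists at the same grade until the woman stops the drug is a tolerability outcome that an extension study is meant to show. An event can also become serious with no change of grade. Protocol 8.3 separates the two ideas itself: "Seriousness (not severity) serves as a guide for defining regulatory reporting obligations". Yet neither becoming serious nor stopping the drug brings a carried-over event into the TEAE set. A reader who turns to Tables 14.3.1.5 and 14.3.1.6 for discontinuations and serious events in A02 would take them as complete when, under the stated rule, they need not be.

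**Working it through.** No formula or stated figure bears on this, so the check follows one event through the definitions and outputs.

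**1. TEAE status, dates known.** (SAP 7.1 treats an AE with a missing or partial date as a TEAE unless it can be shown not to be one.)

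| Event | TEAE in A02? | Tables 14.3.1.5 / 14.3.1.6 and listings |
|---|---|---|
| Onset after first A02 dose | Yes | Eligible |
| Earlier onset, grade rises in A02 | Yes | Eligible |
| Earlier onset, same grade, stops drug in A02 | No | Absent from 14.3.1.5 |
| Earlier onset, same grade, becomes serious in A02 | No | Absent from 14.3.1.6 |

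The last two rows hold whether the event began on 1, 5 or 10 mg or on placebo.

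**2. Does SAP 7.3.2.1 alter this?** Read alone, its first dose could be the A01 dose. But SAP 7.3.1.4 and 7.3.2.3 name A02, and both protocol sections do so in substance. The onset formula in 7.3.2.3 is start date minus first A02 dose date plus 1. An event starting the day before that dose gets −1 + 1 = 0, and earlier ones are negative, so the SAP presumes A02 onset.

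**3. A route created by the protocol.** Week 12 is A02 Visit 1 (Protocol 3.1) and dosing is near bedtime (7.2), so Week 12 assessments come before the first A02 dose.
- Protocol 4.5.2 discontinues a woman from the study for a Week 12 endometrial thickness of 5 mm or more on central reading, or an abnormal adjudicated Week 12 biopsy.
- Protocol 4.5.1 stops medication for a clinically significant breast finding at baseline.
- Protocol 8.8 makes clinically significant endometrial abnormalities AEs.

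If such an AE is dated to the Week 12 assessment, it precedes dosing and is not a TEAE under the protocol, even when the result arrives and stops the drug later. The SAP counts events on or after the first dose, so comparing dates alone might capture a same-day event. The SAP does not say whether time of onset is used. Endometrial and breast safety are both listed among the primary safety endpoints.

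**4. Where the omitted event still appears.**
- All-AE listing: yes, with seriousness and action taken, provided it is recorded as an AE.
- Disposition: yes, if she leaves the study. Protocol 4.5.1 asks that women who stop treatment stay on study, so a drug stop alone may not show there. Disposition gives reasons, not System Organ Class and Preferred Term.
- Tables 14.3.1.9 and 14.3.1.10: possibly, if judged related (and serious, for the second). Their titles and SAP 7.3.2.2 carry no TEAE limit, but 8.2.1 opens as a TEAE summary.
- If judged unrelated: no readable AE summary table. Some 8.2.1 items are redacted and cannot be assessed.

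**5. Can the number be estimated?** No. The documents do not give the share of A01 AEs still ongoing at Week 12, or the share that later stop drug or turn serious. SAP 8.5 gives A01 AE incidence of 64.3% on 10 mg, but only for sites other than the four Florida ones, where it was 4.3%. If 10% to 30% of 10 mg entrants came from those four sites (assumed), the blended rate would be 0.9 × 64.3 + 0.1 × 4.3 = 58.3% down to 0.7 × 64.3 + 0.3 × 4.3 = 46.3%. Even that describes all A01 subjects, whereas A02 takes only completers. The 364 entrants are a ceiling, with no split by arm.

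**The case against.** The strongest reply is that nothing is lost. Every AE is listed in full, deaths are listed without a TEAE limit, and discontinuation reasons are tabulated. A clock that starts at the first A02 dose is also a reasonable choice, because all entrants began the same open-label 10 mg regimen. These points stand, and they keep the matter modest. They do not close the gap: a full listing is not a summary, and disposition neither codes the event nor reliably records a drug stop without study withdrawal.

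A reader might infer three stronger things that the documents do not support.
- **That these events vanish from every AE table.** The two adverse drug reaction tables are not TEAE-limited by their wording, and redacted outputs cannot be judged.
- **That the rule makes women from the A01 active arms look better tolerated.** It also excludes events begun on A01 placebo. Carry-over may differ by arm, but no figure shows that it does.
- **That onset must be re-counted from the first MT-8554 dose.** The same A02 day does mean different cumulative exposure for former placebo and former active women, but the TEAE summaries are already split by A01 arm and only the overall column mixes them. A re-clocked version would put several dose levels on one clock. It is a preference, not a correction.

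**Conclusion.** The point holds for the discontinuation and serious-event tables and their listings. Applied as written, the rule omits any carried-over event of unchanged grade that stops study drug or becomes serious in A02, and the protocol's own Week 12 criteria give a realistic route to such cases. This rests on reading the SAP's first dose as the A02 dose, on known onset dates, and on the table titles meaning what they say. The error can only be an undercount. Its size is unknown, and any count of lost discontinuations would rest on persistence and stopping rates for which the documents give no source. The change is worth making because safety is the primary objective and the remedy is cheap. The gap does not undermine the study.

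**What to change.** In SAP 8.2.1, build Tables 14.3.1.5 and 14.3.1.6 and their listings from all AEs, regardless of TEAE flag or onset study, or add companion versions that do so. Include an AE if:
- the action taken was withdrawal of study drug in A02; or
- it was reported as serious during A02, meaning an SAE report dated on or after the first A02 dose.

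Mark those with onset before the first A02 dose. The SAE report date is suggested because the AE record described in Protocol 8.6 lists seriousness but no date of becoming serious. It is a proxy, since Protocol 8.7 counts its 24 hours from the investigator's awareness.

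Two wording changes go with this: name A02 in the SAP 7.3.2.1 TEAE definition, and state whether 14.3.1.9 and 14.3.1.10 are limited to TEAEs. Keep the A02 clock for the other tables. A version counted from the first MT-8554 dose is optional under Protocol 10.3.1.

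The cost is SAP wording, minor programming, and possibly slightly higher discontinuation and serious-event counts. Action taken and seriousness are already recorded for each AE.
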